| 06              | 04-Oct-2016    | 
Change 1
 
Change: The number of specimens to be collected per site has been increased from approximately 40-55 to approximately 100.
 
Reason: To allow for collecting an increased number of samples and samples sourced by the clinical sites.
 
Justification: To provide sufficient number of specimens to cover the range of concentrations required for the three study analytes.
 
Change 2
 
Change: Extended the duration of the study from 10 weeks to 16 weeks.
 
Reason: To ensure all samples needed per the study protocol are obtained and received and tested by the clinical sites.
 
Justification: To allow for completion of all study related activities within the given timeframe of the study protocol.
 |

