## **B. Statistical Analysis Description (Method Comparison)**

### **1. Study Design**

Method comparison testing will be performed using whole blood capillary specimens prospectively collected from routine patient care. This testing will be performed at a minimum of 3 sites. For each assay (glucose, hematocrit and sodium), testing of approximately 120 native and altered specimens will be performed in singlicate on both the i STAT 500 analyzer and the i STAT 1 Wireless analyzer. One (1) i-STAT 500 and one (1) i-STAT 1 Wireless analyzer will be used for this testing. Each site should collect and test approximately 100 specimens until sufficient specimens are collected and tested for study analysis. A minimum of one lot of i STAT EC4+ cartridges will be used for this testing.

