It is expected that specimen collection will be completed at different times for each of the three assays (sodium, glucose and hematocrit) during the study. The data for a given assay may be analyzed against acceptance criteria once the specimen collection for that assay has been completed and may be used for different regulatory submissions (i.e. FDA response or 510(k) submission). Once specimen collection is determined to be completed, additional specimens will not be collected for that assay unless requested by a regulatory agency.

Interim data for a given assay (before specimen collection is completed) will not be evaluated against acceptance criteria. Interim data monitoring will be conducted to ensure the data meets validity criteria and minimum sample size requirements.

CONFIDENTIAL INFORMATION

III. Statistical Procedures

Refer to the clinical evaluation protocol for the objective of the study, study design, and for additional details on data handling conventions. This section contains additional details about the analyses in the clinical study plan, as well as other additional analyses needed for the regulatory submission(s).

A. Method Comparison

1. Glucose

a. Study Design

Method comparison testing will be performed using whole blood capillary specimens prospectively collected from routine patient care. This testing will be performed at a minimum of 3 sites. Testing of approximately 120 native and altered specimens will be performed in singlicate on both the i-STAT 500 analyzer and the i-STAT 1 Wireless analyzer. One (1) i-STAT 500 and one (1) i-STAT 1 Wireless analyzer will be used for this testing. Each site should collect and test a minimum of 40 specimens until sufficient specimens are collected and tested for study analysis. A minimum of one lot of i-STAT EC4+ cartridges will be used for this testing.

b. Analysis Variables

The analysis variable for the method comparison study is the i-STAT EC4+ cartridge glucose concentration values (mg/dL).

c. Sample Size

The sample size is based on the recommendation of CLSI EP09-A3.

A minimum of 120 capillary whole blood specimens covering the measuring interval will be collected from a minimum of 3 sites. Each site should collect a minimum of 40 specimens.

Minimum of 3 sites

Within each site:

Number of lots = 1

i-STAT 1 Wireless analyzers = 1

i-STAT 500 analyzers = 1

Replicates per specimen = 1

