 - 1) Compute the average bias across all the specimens (\bar{d}) and the SD corresponding to the bias.
 - 2) Find the maximum scaled difference (ESD_1) as follows:
$$ESD_1 = \max |d_j - \bar{d}| / SD \quad \text{for } j = 1, 2, \dots, n$$
- 3) Repeat this calculation to obtain the ESD_i for all potential outliers ($i = 1, 2, \dots, h$). Each subsequent calculation of ESD_i is performed after removing the previously identified potential outlier from the dataset. Thus at each iteration the number of results is reduced by one, then \bar{d} , SD, and the maximum scaled difference (ESD_i) are computed again (ie, to look for outlier 2, the number of samples remaining is $j = 1, 2, \dots, n-1$).
- 4) For $i = 1, 2, \dots, h$, compute the following critical values:

$$\lambda_i = \frac{t_{v,p} (n - 1)}{\sqrt{(n - i + 1)(v + t_{v,p}^2)}}$$

where

n = the initial number of samples in the dataset

$i = 1, 2, \dots, h$

$v = n - i - 1$

$$p = \frac{\alpha}{2(n - i + 1)}$$

$t_{v,p}$ = 100p percentage point from Student's t distribution with v , degrees of freedom and probability = p .

- iv The number of outliers is determined by finding the largest i such that $ESD_i > \lambda_i$.

h. Acceptance Criteria

For method comparison, acceptance criterion will be applied to Passing-Bablok regression result for the single replicate result from the i-STAT 500 vs. the single replicate result from the i-STAT 1 Wireless for the entire measuring interval. Samples across the measuring interval shall have a regression slope of 1.0 ± 0.054 and correlation coefficient (r) ≥ 0.95 (DIR-001, CartP_145).

CONFIDENTIAL INFORMATION

There is no acceptance criterion for other analyses. The information is intended to be reported in regulatory submission(s) and/or product labeling.

3. Sodium

a. Study Design

Method comparison testing will be performed using whole blood capillary specimens prospectively collected from routine patient care. This testing will be performed at a minimum of 3 sites. Testing of approximately 120 native and altered specimens will be performed in singlicate on both the i-STAT 500 analyzer and the i-STAT 1 Wireless analyzer. One (1) i-STAT 500 and one (1) i-STAT 1 Wireless analyzer will be used for this testing. Each site should collect and test a minimum of 40 specimens until sufficient specimens are collected and tested for study analysis. A minimum of one lot of i-STAT EC4+ cartridges will be used for this testing.

b. Analysis Variables

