The analysis variable for the method comparison study is the i-STAT EC4+ cartridge sodium concentration values (mmol/L).

c. Sample Size

The sample size is based on the recommendation of CLSI EP09-A3.

A minimum of 120 capillary whole blood specimens covering the measuring interval will be collected from a minimum of 3 sites. Each site should collect a minimum of 40 specimens.

Minimum of 3 sites

Within each site:

Number of lots = 1

i-STAT 1 Wireless analyzers = 1

i-STAT 500 analyzers = 1

Replicates per specimen = 1

A suggested distribution of specimen target levels for sodium by site is presented in the chart below:

CONFIDENTIAL INFORMATION

Sodium (mmol/L)	~ # Sample /Site	Max # Samples /Site
≤ 130	8	14
> 130-140	16	24
> 140-150	12	20
> 150	4	8
Total	40	

If more than the maximum allowed number of samples is collected for a given sodium range within a site, the sodium result from samples with the earlier collection date and time will be included in the analysis. The sodium results for samples collected beyond the maximum allowed number of samples will not be used for this analysis.

d. Statistical Analysis Method

Perform the following analyses for the single replicate of the i-STAT 500 result versus the single replicate of the i-STAT 1 Wireless result. Analyses will be done with outliers and without outliers if any outliers are identified.

- For each site as well as all sites combined, calculate the correlation coefficient and perform the Deming regression and Passing-Bablok regression analyses on the concentration values (the i-STAT 500 result as dependent variable versus the i-STAT 1 Wireless result as independent variable) and provide estimates and 95% CIs of the slope and intercept from the regression analysis.
- For each site as well as all sites combined, generate scatter plots of the concentration values of the i-STAT 500 result (y-axis) versus the concentration values of the i-STAT 1 Wireless result (x-axis). The line of identity ($y = x$) and descriptive statistics will be presented in the scatter plots.

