- For each site as well as all sites combined, generate Bland-Altman bias plots and Bland-Altman percent bias plots. Calculate the difference between the i-STAT 500 concentration value (y) and the i-STAT 1 Wireless concentration value (x), $y - x$. Also calculate $(y + x) / 2$. Plot the difference between y and x, $y - x$, against their mean $(y + x) / 2$ (Bland-Altman bias plot); Plot the percent difference between y and x, $100 \times (y - x) / x$, against their mean $(y + x) / 2$ (Bland-Altman percent bias plot).
- Using the regression equation for each site separately and for all sites combined, calculate the predicted bias (difference) between the i-STAT 500

CONFIDENTIAL INFORMATION

results and the i-STAT 1 Wireless results at the medical decision points (115, 135, 150 mmol/L) and their 95% CIs. The calculation of predicted bias and its 95% CI calculation are based on CLSI EP09-A3.

e. Level of Significance

Two-sided confidence intervals will be calculated at a 95% confidence level.

f. Data Handling Convention

All results from this testing that are performed according to the protocol and not excluded by the reviewers will be eligible for analysis. Reasons for any excluded results will be captured in the study database.

- Exclude the specimen from analysis if no results can be obtained from either the i-STAT 1 Wireless or the i-STAT 500.
- Exclude test results if there is an assignable cause.
- Exclude the specimen if the sodium concentration value is outside of the measuring interval on either analyzer.
- Exclude a second valid result obtained due to a repeat test of the same specimen for another analyte. These results will be excluded with the reason “Additional test for other analyte. Repeat testing produces results for all analytes on cartridge.”
- Exclude a result obtained from a subject that is for a bucket that is already filled with the reason “Not part of analysis.”

g. Outliers

The outlier criteria below are based on CLSI document EP09-A3 Appendix B. The generalized Extreme Studentized Deviate (ESD) technique will be used to detect the outlier.

The generalized Extreme Studentized Deviate (ESD) technique assumes that the distribution of the vast majority of data points is normal (Gaussian), can be used when the number of outliers is unknown and becomes more robust as the number of samples increases. To perform this technique:

CONFIDENTIAL INFORMATION

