- i Set the significance level $\alpha = 0.01$, which will be used to detect outliers.
- ii No more than 5% of sample results can be flagged as outliers. Set the upper bound on number of potential outliers (h) at this 5% level, rounding down to a whole number ($h = 6$ for 120 samples).
- iii Determine if one or more suspect results could be outliers based upon the generalized Extreme Studentized Deviate (ESD) test.
 - 5) Compute the average bias across all the specimens (\bar{d}) and the SD corresponding to the bias.
 - 6) Find the maximum scaled difference (ESD_1) as follows:
$$ESD_1 = \max |d_j - \bar{d}| / SD \quad \text{for } j = 1, 2, \dots, n$$
- 7) Repeat this calculation to obtain the ESD_i for all potential outliers ($i = 1, 2, \dots, h$). Each subsequent calculation of ESD_i is performed after removing the previously identified potential outlier from the dataset. Thus at each iteration the number of results is reduced by one, then \bar{d} , SD, and the maximum scaled difference (ESD_i) are computed again (ie, to look for outlier 2, the number of samples remaining is $j = 1, 2, \dots, n-1$).
- 8) For $i = 1, 2, \dots, h$, compute the following critical values:

$$\lambda_i = \frac{t_{v,p} (n - 1)}{\sqrt{(n - i + 1)(v + t_{v,p}^2)}}$$

where

n = the initial number of samples in the dataset

$i = 1, 2, \dots, h$

$v = n - i - 1$

$$p = \frac{\alpha}{2(n - i + 1)}$$

$t_{v,p}$ = 100p percentage point from Student's t distribution with v , degrees of freedom and probability = p .

- iv The number of outliers is determined by finding the largest i such that $ESD_i > \lambda_i$.

h. Acceptance Criteria

For method comparison, acceptance criterion will be applied to Passing-Bablok regression result for the single replicate result from the i-STAT 500 vs. the single replicate result from the i-STAT 1 Wireless for the entire measuring interval. Samples across the measuring interval of 100 – 180 mmol/L shall have a regression slope of 1.0 ± 0.05 and correlation coefficient (r) ≥ 0.95 (DIR-001, CartP_74).

CONFIDENTIAL INFORMATION

There is no acceptance criterion for other analyses. The information is intended to be reported in regulatory submission(s) and/or product labeling.

IV. References

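### Sodium: do the per-site maximums in the outer ranges (≤130 and >150 mmol/L) throw away slope precision that the trial needs?

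*SAP*

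**What the plan says.** SAP III.A.3.c (Sodium, Sample Size) sets a suggested count and a maximum per site for four ranges:

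| Range (mmol/L) | Suggested | Maximum |
|---|---|---|
| ≤130 | 8 | 14 |
| >130–140 | 16 | 24 |
| >140–150 | 12 | 20 |
| >150 | 4 | 8 |
| Sum | 40 | 66 |

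If a range overflows, "the sodium result from samples with the earlier collection date and time will be included in the analysis". SAP III.A.3.f repeats the rule: "Exclude a result obtained from a subject that is for a bucket that is already filled". The protocol has the same filled-bucket exclusion in IX.B.6. No range is exempt.

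On numbers, SAP 3.c says "A minimum of 120 capillary whole blood specimens covering the measuring interval will be collected", and SAP 3.a says "Each site should collect and test a minimum of 40 specimens until sufficient specimens are collected and tested for study analysis". Protocol IX.B.1 (version 6) says "Each site should collect and test approximately 100 specimens until sufficient specimens are collected and tested for study analysis". The protocol's revision history justifies the rise from about 40–55 to about 100 per site in these words: "To provide sufficient number of specimens to cover the range of concentrations required for the three study analytes". SAP section II closes collection assay by assay: "Once specimen collection is determined to be completed, additional specimens will not be collected for that assay unless requested by a regulatory agency".

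Acceptance (SAP 3.h) rests on the Passing-Bablok slope (1.0 ± 0.05) and r ≥ 0.95: "Samples across the measuring interval of 100 – 180 mmol/L shall have a regression slope". Predicted bias at the decision points, including 115 mmol/L, is reported without a criterion.

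**The concern.** In a regression, precision of the slope comes from the extremes. The two outer ranges span 60 of the 80 mmol/L in the measuring interval and contain the decision point 115. The maximums sit in a SAP written for at least 40 specimens per site, which cites protocol V2. Version 6 raised the number to about 100 in order to cover the range. It then looks as if the SAP discards the very pairs that the protocol change was meant to gain. At stake would be a wider interval for the slope and for bias at 115, and a somewhat higher chance that an analyzer with a wrong slope passes. If the most extreme specimens came last, the earliest-first rule would also narrow the range analysed.

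**Working it through.** **The plan's own figure.** 8 + 16 + 12 + 4 = 40 per site, and 3 sites × 40 = 120. This matches the stated minimum.

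**When the outer maximums bind.** In SAP proportions (20% and 10%) they bind above 14/0.20 = 70 and 8/0.10 = 80 specimens per site. At 40–70 per site the expected loss in the outer ranges is nil.

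**Unfavourable case: 100 per site in SAP proportions (assumed).** Expected counts are 20/40/30/10 and kept counts 14/24/20/8 = 66. Per site 6 + 2 = 8 of 30 outer pairs are dropped, so 24 of 90 over three sites.

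**Effect on the slope.** The standard error (SE) is proportional to 1/√Sxx, with Sxx = Σ nₖ[(mₖ − mean)² + wₖ²/12] for range midpoints mₖ and widths wₖ. Values are assumed uniform within ranges. With the outer ranges taken as 100–130 and 150–180, the midpoints are 115, 135, 145, 165 and wₖ²/12 is 75, 8.33, 8.33, 75.

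- Required 120 (24/48/36/12), mean 137: Sxx = 24(484+75) + 48(4+8.33) + 36(64+8.33) + 12(784+75) = 13,416 + 592 + 2,604 + 10,308 = 26,920.
- Capped 198 (42/72/60/24): Sxx = 49,286.
- Outer maximums lifted, 222 pairs (60/72/60/30): Sxx = 64,445.

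| Comparison | Outer values 100–130, 150–180 | Outer values 125–130, 150–155 |
|---|---|---|
| SE, capped vs outer pairs kept | √(64,445/49,286) = 1.14 | √(17,798/14,440) = 1.11 |
| SE, required 120 vs capped | √(49,286/26,920) = 1.35 | √(14,440/8,132.5) = 1.33 |

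Simulations that let the counts vary at random gave up to 1.18 for the first row. The outer ranges hold 65–88% of Sxx in the suggested distribution, so the premise about slope information is right.

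**Does it threaten the decision?** The 95% half-width of the slope in the capped set is 1.96 × SD of the difference/√Sxx. With an assumed SD of 1–2 mmol/L it runs from 1.96 × 1/√49,286 = 0.009 to 1.96 × 2/√14,440 = 0.033. With an error SD of 2 on each result, the SD of the difference is 2√2 = 2.83 and the largest value is 0.046. All lie inside ±0.05.

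Simulated acceptance of a true slope of 0.93 (800 runs per setting; outer values even with SD 1, even with SD 2, thinning out with SD 1, thinning out with SD 2):

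- required 120: 8, 25, 19, 31%
- capped: 2, 15, 12, 30%
- outer pairs kept: 1, 12, 7, 27%

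At a true slope of 0.90 the capped set accepts in 0–1%. With order unrelated to value, the mean slope is the same with and without the outer caps, and a correct analyzer passes in over 99% of runs either way.

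**Is 100 per site in SAP proportions likely?** In those proportions 40 per site already meets every sodium target, so an increase made to cover the range suggests that some ranges were filling more slowly. This is an inference, because the justification covers three analytes jointly. If 100 specimens were needed to reach the sodium targets of 8 and 4, the outer shares would be 8/100 = 8% and 4/100 = 4%.

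Binomial chance that a site exceeds its maximum at 100 specimens:

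| Outer shares | ≤130 (more than 14) | >150 (more than 8) |
|---|---|---|
| 20%, 10% | 92% | 68% |
| 15%, 7.5% | 54% | 34% |
| 10%, 5% | 7% | 6% |
| 8%, 4% | 1.3% | 1.9% |

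At 10% and 5%, the mean loss over three sites is about 0.8 of 45 outer pairs and the slope SE rises by a factor of 1.01. At 15% and 7.5% the factor is 1.04–1.06.

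**The case for a change.** The case for a change is that the outer pairs are valid and already tested, that they are the most informative ones, and that a few sentences in the SAP would keep them at no cost in specimens. The coverage requirement attaches to the specimens collected, so no other sodium rule protects coverage in the set analysed. Contriving is allowed where target levels cannot be sourced, so extreme specimens might arrive late. If they came last at every site, the slope SE would rise by a factor of 1.31–1.35. In the harshest simulated setting (thinning values, error SD 2) a correct analyzer would pass in 83% rather than 100% of studies, because r falls close to 0.95.

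The reading of the text and the arithmetic stand. So does the observation that the SAP still cites protocol V2, which is a clerical matter. The rest does not carry. The 83% needs both over-filled outer ranges and extremes last at all sites, and the documents state neither. Contriving serves levels that cannot otherwise be filled, so there is little reason to contrive into a range that is already full.

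Lifting the caps has costs too. The outer share would rise from 66/198 = 33% to 90/222 = 41%, against 36/120 = 30% in the suggested distribution. That gives more weight to high-leverage specimens, some contrived with the sponsor's help. It would raise r, itself an acceptance statistic, and leave the number of such specimens open until the sponsor declares collection complete. A prespecified maximum with a collection-time rule fixes membership of the set without reference to the difference between analyzers. Excluded results are also listed with reasons (SAP section II), so they stay visible.

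**Conclusion.** The concern does not hold. It measures the capped set against a surplus that the plan never required. Against the required 120 pairs, the capped set in the concern's own scenario has about 198 pairs and the smaller slope SE. The loss relative to keeping the outer pairs is 11–18% in SE if 100 specimens per site fall in SAP proportions. It is about 1% if the outer shares are 10% and 5%, and nil in expectation up to 70 per site. With collection order unrelated to value there is no bias and no material effect on whether a correct analyzer passes.

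These figures rest on assumed error SDs and assumed spreads within ranges, since the documents give neither. The comparison with the required 120 held for both spreads shown, from the full interval to outer values within 5 mmol/L of the range edge. Whether to cap the outer ranges is a design choice on which reasonable statisticians may differ, and the plan made it in advance.
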